2 SAMPLE SIZE DETERMINATION

Part B will enroll approximately 23 participants. The sample size is designed to provide an estimate of the true response rate. If 5 responders are observed out of 23 treated participants, the observed response rate is 22% (90% CI: 9%, 40%), with the lower bound of the exact 90% CI exceeding 8%, which is the historical standard of care response rate estimated from a pooled analysis of 8 randomized studies in ITP participants.

28-Nov-2022 Version number: 1

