4.3.2 Main analytical approach

The responder of the primary endpoint must have met ALL of the following criteria:

 Platelet counts ≥ 50,000/µL for at least 8 out of the last 12 weeks [Week 14 (Day 92) to Week 25 (Day 169)] during the 24-week treatment period (or equivalently the ontreatment period for efficacy).

The on-treatment period for efficacy is defined as the period from the date of the 1st IMP administration

- up to 1 day after the last IMP administration for participants who did not enter LTE, or
- Week 25 (Day 169) visit for participants who entered LTE.

The on-treatment period for efficacy will be used for all efficacy analyses related to platelet counts.

And,

- Not rescued after 10 weeks of treatment. "Rescued after 10 weeks of treatment" for efficacy analysis is defined as from Week 11 (Day 71) to the day prior to the last date of IMP administration for those do not enter LTE or the visit date of Week 25/C1D1_LTE (Day 169) for those entered LTE.
- Not discontinued before Week 25 due to related TEAE (per investigator's assessment), lack of response, or need to rescue medication as recorded in eCRF, i.e., participants who discontinue before Week 25 and the discontinuation reasons are treatment related adverse event (AE), lack of response, or need of rescue medication will be considered as non-responders.

The response rate will be summarized for ITT population along with the 95% exact Clopper-Pearson Confidence Interval (CI).

Platelet counts and the change from baseline will be summarized by visit. The time course of platelet count will be described graphically, and the following plots will also be provided:

- Individual platelet count profile: line plot of platelet count by visit for each participant
- Spaghetti plot platelet count by participant in each study period (i.e., main and LTE)
- Median platelet count/change from baseline by visit in each study period

Property of the Sanofi group - strictly confidential

28-Nov-2022 Version number: 1

An unscheduled platelet count will be allocated to a scheduled visit if it is within the visit window of the scheduled visit where a platelet count is not available (see Section 5.3).

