4.3.4 Supplementary analysis

The following supplementary analyses will be performed to further evaluate the durable platelet response during the 24-week treatment period. The proportion will be summarized along with the 95% exact Clopper-Pearson CI for the ITT population.

- Proportion of participants who have met the primary endpoint (Section 4.3.2) or entered LTE,
- Number/proportion of participants able to achieve platelet counts ≥ 50,000/µL for ≥two-thirds of at least 8 non-missing weekly scheduled platelet measurements during the last 12 weeks of the 24-week treatment period without the use of rescue medication after 10 weeks of active treatment, provided that at least 2 non-missing weekly scheduled platelet measurements are at or above 50,000/µL during the last 6 weeks of the 24-week treatment period.

To qualify for a responder, a participant must have met the following criteria

- At least 8 non-missing weekly scheduled platelet measurements during the last 12 weeks of the 24-week treatment period, and
- Platelet counts $\geq 50,000/\mu L$ for \geq two-thirds of 8 non-missing weekly assessments, and
- at least 2 platelet counts ≥50,000/μL occurred during the last 6 weeks of the 24-week treatment period, and
- Not rescued after 10 weeks of treatment (see Section 4.3.2 for details), and
- Not discontinued before Week 25 due to related TEAE (per investigator's assessment), lack of response, or need of rescue medication as recorded in eCRF.

The last 6 weeks are Week 20 (Day 134) to Week 25 (Day 169).

• Number/proportion of participants able to achieve platelet counts ≥50,000/μL on at least 4 out of the last 6 biweekly platelet counts during the 24-week treatment period without the use of rescue medication after 10 weeks of active treatment.

To qualify for a responder, a participant must have met the following criteria

- Platelet counts $\geq 50,000/\mu L$ for at least 4 out of the last 6 biweekly platelet counts during the 24-week treatment period, and
- Not rescued after 10 weeks of treatment (see Section 4.3.2 for details), and

28-Nov-2022 Version number: 1

- Not discontinued before Week 25 due to related TEAE (per investigator's assessment), lack of response, or need of rescue medication as recorded in eCRF.

The last 6 biweekly counts will be at Weeks 15, 17, 19, 21, 23, and 25.

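### Part B SAP 4.3.4: the definition and the responder checklist of the second supplementary analysis use different denominators, so participants with 10 to 12 available counts could be classified differently

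*SAP*

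**What the plan says.** Part B SAP 4.3.4 lists three supplementary analyses of durable platelet response, each a proportion of the ITT population with an exact 95% interval. The second is first defined in a sentence that sets the required fraction as "two-thirds of at least 8 non-missing weekly scheduled platelet measurements during the last 12 weeks" of treatment. On that wording the denominator is the number of available counts, with a floor of 8.

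A checklist of responder criteria follows. Its first item gives the floor separately: "At least 8 non-missing weekly scheduled platelet measurements during the last 12 weeks of the 24-week treatment period, and". Its second item then sets the fraction as "two-thirds of 8 non-missing weekly assessments". The remaining items require at least 2 qualifying counts in the last 6 weeks (Week 20 to Week 25), no rescue after 10 weeks of treatment, and no discontinuation before Week 25 for a related TEAE, lack of response or need for rescue medication.

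For comparison, the primary endpoint (4.3.2) requires qualifying counts in at least 8 of the 12 weeks from Week 14 to Week 25. The third supplementary analysis requires 4 of the last 6 biweekly counts.

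**The concern.** The definition has a denominator that varies from 8 to 12. The checklist, taken literally, has a denominator fixed at 8. A checklist is the natural source for programming a responder flag, and nothing in 4.3.4 says the definition prevails. Two programmers could each follow the text and report different rates.

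The affected participants are those with the most complete data. Section 4.3.3 plans no sensitivity analysis of the primary endpoint, so the supplementary analyses are what a reader has beside the primary rate. Of the three, this is the only one with an explicit non-missing denominator. If it gave a higher rate than the primary, the reader could not tell whether that came from the handling of missing counts or from a lower bar.

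**Working it through.** **Plan's own figure.** The SAP gives no numerical result for this analysis, so there is none to reproduce. The planned size of 23 comes from the Part B sample-size section. Its precision statement does reproduce: 5/23 = 21.7%, exact 90% interval 8.98% to 40.4%, against the stated 22% (9% to 40%).

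**Inputs.** Required fraction 2/3 and minimum of 8 available counts (4.3.4); at most 12 weekly counts, Week 14 to Week 25 (4.3.2); n = 23.

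**Counts needed.** Let m be the number of non-missing counts.

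- Definition: the smallest whole number not below 2m/3.
- Checklist, read as any 6 qualifying counts: 2 × 8/3 = 5.33, so 6 at every m.

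| m | 2m/3 | Definition needs | Checklist needs (any-6 reading) | Checklist share of m | Gap |
|---|---|---|---|---|---|
| 8 | 5.33 | 6 | 6 | 75% | 0 |
| 9 | 6.00 | 6 | 6 | 67% | 0 |
| 10 | 6.67 | 7 | 6 | 60% | 1 |
| 11 | 7.33 | 8 | 6 | 55% | 2 |
| 12 | 8.00 | 8 | 6 | 50% | 2 |

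**Which rule fits the rest of the section.** The primary rule is 8/12 = 2/3 and the third supplementary rule is 4/6 = 2/3. With all 12 counts present, the definition also needs 8. The first 6 weeks can supply at most 6 of those 8, so at least 2 must fall in the last 6 weeks and the late-response condition is met automatically. With complete data the definition therefore reduces to the primary count rule. The any-6 reading does not.

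**Another literal reading.** Suppose the 8 counts were the last 8 (Weeks 18 to 25) of a complete set.

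- Someone with 6 qualifying counts, 4 of them in Weeks 14 to 17, has 2 in the last 8 and fails the checklist.
- Someone with 8 qualifying counts, 4 in Weeks 14 to 17 and 4 in Weeks 18 to 25, meets the definition but has only 4 of the 6 needed from the last 8, and fails the checklist.

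The fixed denominator can thus be looser or stricter than the definition, depending on which 8 are meant.

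**Size per participant.** 1/23 = 4.3 percentage points.

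**Illustration only.** Assume 12 counts, independent within a participant, with weekly probability p of reaching 50,000/µL. The documents give neither assumption. Including the late-response condition, the chance of meeting the count criteria is:

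| p | Definition | Checklist (any 6) |
|---|---|---|
| 0.3 | 0.01 | 0.11 |
| 0.4 | 0.06 | 0.33 |
| 0.5 | 0.19 | 0.60 |
| 0.6 | 0.44 | 0.83 |
| 0.7 | 0.72 | 0.96 |

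Independence of weekly counts within a patient is artificial. The table shows only that the gap is not negligible for intermediate responders; it does not forecast the trial's rates.

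**The case against.** The best defence is that the number 8 in the second item is shorthand for the set named in the item just above it, or that the words for a minimum were dropped. Both are plausible. The definition stands directly above the checklist and is the only version that works for every number of available counts. This lowers the chance that the looser rule was intended, but it leads to the same correction.

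A ≥ sign might also have been lost when the PDF was converted to text. That is not shown. Operators do appear to be missing elsewhere in the same SAP (the LTE rescue window in 4.4.2, the ITP duration formula in Appendix 2), but those look like minus signs or dashes. A look at the original page would settle it.

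Three stronger inferences are tempting, and the documents do not support them:

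- *The checklist lets 6 of 12 counts pass.* That is the most permissive reading. The text does not say which 8 counts apply when more exist.
- *Every participant with complete data and 6 or 7 qualifying counts is misclassified.* The late-response, rescue and discontinuation criteria also apply. Part B allows rescued patients to continue (protocol 4.12.2), so some may have complete data and still be non-responders under both rules.
- *The durability analysis is defeated.* The stated purpose is only to evaluate durable response further. Being looser than the primary is not in itself a fault: the first supplementary analysis also counts anyone who entered the LTE.

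**Conclusion.** The inconsistency is real and minor. Section 4.3.4 gives two rules for one analysis. On the any-6 reading they agree at 8 or 9 available counts and differ by 1 at 10 and by 2 at 11 and 12. A participant with complete data, 6 or 7 qualifying counts and all other criteria met could then be a responder under the checklist but not under the definition or the primary count rule.

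The documents give no basis for estimating how many participants would fall in that gap, so the total effect on the rate is unknown. The conclusion assumes that the checklist line is printed as it reads here and might be coded literally. It concerns one descriptive supplementary proportion and does not touch the primary endpoint, the sample size or the other two supplementary analyses.

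**What to change.** Reword the second checklist item to: platelet counts ≥50,000/µL for at least two-thirds of all non-missing weekly scheduled assessments in the last 12 weeks (minimum 8 non-missing). This matches the definition and, with complete data, the primary count rule.

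If the analysis has already been run, state in the report which rule was coded. If it was the checklist, give the rate under the definition as well.

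The cost is a few words and at most one re-run of a responder flag, with no new data. Under the any-6 reading every definition responder is also a checklist responder, so the corrected rate cannot be higher and may be slightly lower.

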4.3.5 Subgroup analyses

Analyses will be performed to assess the consistency on the primary endpoint (Section 4.3.2) across the following subgroups:

- Duration of ITP Disease: Persistent vs Chronic, where
 - Persistent: between 3-12 months from date of ITP diagnosis
 - Chronic: > 12 months from date of ITP diagnosis
- Duration of ITP: ≤ 3 years vs > 3 years
- Type of Prior ITP Therapy
 - Prior thrombopoietin receptor agonist (TPO-RA) but no prior corticosteroid (CS)
 - Prior CS but no prior TPO-RA
 - Prior TPO-RA and prior CS
 - Neither TPO-RA nor CS
- Prior TPO-RA
 - TPO-RA naïve, i.e., never received TPO-RA medications, Yes vs No
 - For non-TPO-RA naïve, responded to TPO-RA, Yes vs No

Note: "responded" means "resulted in platelet count ≥50,000/µL" per eCRF.

- Prior CS
 - Prior CS, Yes vs No
 - For those who exposed to CS, responded to CS, Yes vs No
- Prior IVIg or Anti-D immunoglobulin
 - Prior IVIg or Anti-D immunoglobulin, Yes vs No
 - For those who exposed to IVIg or Anti-D immunoglobulin, responded to either, Yes vs No
- Prior Rituximab
 - Prior Rituximab, Yes vs No
 - For those who exposed to Rituximab, responded to Rituximab, Yes vs No
- Participants on rilzabrutinib monotherapy vs. Participants on ITP concomitant therapy
- Participants on concomitant ITP medication
 - TPO-RA but no CS

Property of the Sanofi group - strictly confidential

- CS but no TPO-RA
- TPO-RA and CS
- No concomitant TPO-RA nor CS
- Participants with unique number of prior ITP medications by category: ≤ 3 vs ≥ 3 , and the unique ITP medications is identified by standardized medication name
- Baseline Platelet Count: <15,000/μL vs. ≥15,000/μL
- Splenectomy Yes vs splenectomy No
- Participants who had completed 24 weeks of treatment

95% confidence intervals will be calculated for the proportions using the Clopper-Pearson method.

4.4 SECONDARY ENDPOINT(S) ANALYSIS

4.4.1 Definition of endpoint(s)

The secondary endpoints are defined below:

- Number of weeks with platelet count ≥50,000/μL OR ≥30,000/μL and doubling the baseline in the absence of rescue therapy (platelet counts will be censored for 4 weeks after the use of rescue medication, if given)
- Proportion of all treated participants able to achieve two or more consecutive platelet counts, separated by at least 5 days of ≥50,000/μL AND an increase of platelet count of ≥20,000/μL from baseline without use of rescue medication in the 4 weeks prior to the latest elevated platelet count
- Number of weeks with platelet counts ≥30,000/µL and doubling from baseline over the 24-week treatment period (platelet counts will be censored for 4 weeks after the use of rescue medication, if given)
- Proportion of participants receiving rescue medication
- Change from baseline in ITP Bleeding Scale (IBLS)

4.4.2 Main analytical approach

All secondary endpoints will be assessed during the 24-week treatment period unless otherwise specified. The number (percent) will be summarized for the ITT population along with the 95% exact Clopper-Pearson CI for the categorical endpoints.

• Number of weeks with platelet count ≥50,000/μL OR ≥30,000/μL and doubling the baseline in the absence of rescue therapy (platelet counts will be censored for 4 weeks after the use of rescue medication, if given)

Property of the Sanofi group - strictly confidential

To qualify for the criteria specified in the endpoint at a given week, the participant must have met ALL the following criteria,

- Platelet count ≥50,000/μL OR ≥30,000/μL and doubling the baseline at a given week during the 24-week treatment period from Week 2 (Day 8) to Week 25 (Day 169),
- Not rescued within the 4 weeks prior to the elevated platelet count at the given week, that is, if the participants received rescue medication during the 24-week treatment, platelet counts will be censored from the date when the rescue medication is initiated up to 4 weeks after the use of rescue medication, i.e., any weeks that fall into this period will be considered as not qualifying for the criteria specified.

95% CI of mean using t-distribution will be provided.

• Number of weeks with platelet counts ≥30,000/µL and doubling from baseline over the 24-week treatment period: this endpoint will be derived similarly as the secondary endpoint above.

95% CI of mean using t-distribution will be provided.

• Proportion of all treated participants able to achieve two or more consecutive platelet counts, separated by at least 5 days of $\geq 50,000/\mu L$ AND an increase of platelet count of $\geq 20,000/\mu L$ from baseline without use of rescue medication in the 4 weeks prior to the latest elevated platelet count

To qualify for a responder, the participant must have met the following criteria

[figure not shown]
- \geq 2 consecutive platelet counts \geq 50,000/ μ L, separated by at least 5 days, and
- An increase of platelet count of ≥20,000/μL from baseline, and
- Not rescued within the 4 weeks prior to the latest elevated platelet count
- Proportion of participants receiving rescue medications

The number and proportion of participants receiving rescue medications will be tabulated respectively

- during 24-week treatment period (from the date of first dose of IMP to the day prior to the last date of IMP administration for those do not enter LTE or the visit date of Week 25/C1D1 LTE (Day 169) for those entered LTE)
- during LTE period (from the date of first dose of IMP during LTE to the date of the last dose of IMP 1)
- Change from baseline in ITP Bleeding Scale (IBLS): see Section 4.8.3

[figure not shown]
4.5 EXPLORATORY ENDPOINT(S) ANALYSIS

[figure not shown]
4.5.1 Definition of endpoint(s)

4.5.2 Main analytical approach

[figure not shown]
The general analysis is specified in Section 4.3.2. Necessary details for analyzing each endpoint are provided below.

Property of the Sanofi group - strictly confidential

Page 18

4.6 MULTIPLICITY ISSUES

NA.

Page 76

4.7 SAFETY ANALYSES

All safety analysis will be performed on the safety population as defined in Table 3, unless otherwise specified, using the following common rules:

- The analysis of the safety variables will be essentially descriptive, and no testing is planned unless otherwise specified.
- Safety data in participants who do not belong to the safety population (e.g., exposed but not enrolled) will be provided.

4.7.1 Extent of exposure

The extent of IMP exposure will be assessed by the duration of IMP exposure and treatment compliance and summarized within the safety population. Duration of study drug exposure (days) and treatment compliance will be summarized for main 24-week treatment period and LTE treatment period, respectively.

Duration of IMP exposure

Duration of IMP exposure will be summarized based on treatment periods, which are defined below:

• Duration of study drug exposure in each treatment period (days) = (last IMP administration date during main or LTE treatment period - first IMP administration date in each treatment period) + 1, regardless of unplanned intermittent interruption.

Last dose date can be found in eCRF. If the date of the last dose of IMP is missing, the duration of IMP will be left as missing. In cases where participants are still on-going in LTE when the data base lock (DBL) occurred, the data cut-off date (last participant last visit date in 24-week treatment period) will be used as the last dose date of LTE.

Duration of IMP exposure will be summarized quantitatively and categorically by month: 1 to 28 days (Week 1 to Week 4), 29 to 56 days (Week 5 to Week 8), ..., 141 to 168 (Week 21 to Week 25), 169 to 196 days (Month 1 LTE), 197 to 224 days (Month 2 LTE) etc.

Additionally, the cumulative duration of treatment exposure (expressed in participant-months) will be provided.

Treatment compliance

A given administration will be considered noncompliant if the participant has dates indicating missing doses as recorded in eCRF.

Percentage of treatment compliance for a participant will be defined as the number of administration days that the participant was compliant divided by the total number of administration days (i.e., Duration of IMP) ×100%, during main 24-week treatment period and LTE treatment period, respectively.

28-Nov-2022 Version number: 1

Treatment compliance will be summarized quantitatively and categorically: < 80%, 80% to 100%, and >100%.

4.7.2 Adverse events

General common rules for adverse events

All AEs will be graded according to National Cancer Institute Common Terminology for Adverse Events (NCI-CTCAE) version v5.0, and coded to a lower-level term (LLT), preferred term (PT), high-level term (HLT), high-level group term (HLGT), and associated primary system organ class (SOC) using the Medical Dictionary for Regulatory Activities (MedDRA) currently in effect at Sanofi at the time of the database lock.

The AEs will be analyzed in the following 2 categories:

- Pre-treatment AEs: AEs that developed, worsened, or became serious during the pre-treatment period.
- Treatment-emergent adverse events (TEAE)s: AEs that developed, worsened or became serious during the treatment-emergent period (including the on-treatment and post-treatment periods defined in Section 4.1).

The primary focus of AE reporting will be on TEAEs. Pre-treatment and post-treatment AEs will be flagged in the AE listing.

An AE with incomplete or missing date/time of onset (occurrence, worsening, or becoming serious) will be classified as a TEAE unless there is definitive information to determine it is a pre-treatment AE.

If the assessment of the relationship to IMP is missing for an AE, this AE will be assumed as related to IMP. If the CTCAE grade is missing for 1 of the treatment-emergent occurrences of an AE, the grade will be imputed with the maximal grade of the other occurrences. If the grade is missing for all the occurrences, the grade will be left as missing.

Multiple occurrences of the same event in the same participant will be counted only once in the tables within a treatment phase, using the maximum (worst) grade by treatment phase. Summaries will be provided for all grades combined and for grade ≥ 3 (including grade 5). Missing grades, if any, will be included in the "all grades" category.

The AE tables will be sorted as indicated in Table 4.

Table 4 - Sorting of AE tables

AE presentation	Sorting rules
SOC, HLGT, HLT and PT	By the internationally agreed SOC order and by alphabetic order of HLGTs, HLTs and PTs
SOC and PT	By the internationally agreed SOC order and decreasing frequency of PTs ^a
PT	By decreasing frequency of PTs

a The table of all TEAEs presented by SOC and PT will define the presentation order for all other tables (e.g., treatment-emergent SAE) presented by SOC and PT, unless otherwise specified.

Property of the Sanofi group - strictly confidential

Page 21

Analysis of all adverse events

The overview of TEAE with the details below will be generated:

- Any TEAE
- Any grade \geq 3 TEAE
- Any treatment emergent SAE
- Treatment emergent SAE related to IMP as per Investigator's judgment
- TEAE leading to death
- Grade 5 TEAE (any TEAE with a fatal outcome during the treatment-emergent period)
- Any TEAE leading to permanent IMP discontinuation
- TEAE related to IMP as per Investigator's judgment
- Bleeding events (Intensity Grade 2 or higher)
- Infection (Intensity Grade 2 or higher)

The AE summaries of Table 5 will be generated with number (%) of participants experiencing at least one event. TEAE will be provided for main treatment-emergent period, LTE treatment-emergent period respectively.

Table 5 - Analyses of adverse events

Type of AE	MedDRA levels	Main period	LTE
All TEAE	Overview ^a Primary SOC, HGLT, HLT and PT	✓	✓
	Primary SOC and PT	✓	
	PT	✓	\checkmark
		✓	
TEAE related to IMP as per Investigator's judgment	Primary SOC and PT	✓	✓
TEAE by maximal intensity	Primary SOC and PT	✓	✓
TEAE Grade 3 or higher	Primary SOC and PT	✓	
Treatment emergent SAE	Primary SOC and PT	✓	✓
Treatment emergent SAE related to IMP as per Investigator's judgment	Primary SOC and PT	✓	✓
TEAE leading to permanent discontinuation of intervention	Primary SOC and PT	✓	✓
Bleeding event by grade ^b	Primary SOC and PT	✓	✓
Bleeding events (Intensity Grade 2 or higher) ^b	Primary SOC and PT	✓	✓
Related bleeding events (Intensity Grade 2 or higher) ^b	Primary SOC and PT	✓	✓

28-Nov-2022	
Version number:	1

Type of AE	MedDRA levels	Main period	LTE
Infection (Intensity Grade 2 or higher) ^C	Primary SOC and PT	✓	✓
Related infection (Intensity Grade 2 or higher) $^{\it c}$	Primary SOC and PT	✓	✓
TEAE by age group (<65, >=65 years)	Primary SOC and PT	\checkmark	
TEAE by gender	Primary SOC and PT	✓	
TEAE by concomitant ITP medications (No concomitant ITP medication, CS alone, TPO-RA alone, CS + TPO-RA)	Primary SOC and PT	✓	

a Will include the following AE categories: any AEs, any serious AEs, any AEs leading to death, any AEs leading to permanent intervention discontinuation

Analysis of deaths

Death will be listed.

